7.2.1.3. Overdose

Overdose, as defined for this protocol, refers to luspatercept dosing only. On a per dose basis, an overdose is defined as the following amount over the protocol-specified dose of luspatercept assigned to a given patient, regardless of any associated adverse events or sequelae.

SC 10% over the protocol-specified dose

On a schedule or frequency basis, an overdose is defined as anything more frequent than the protocol required schedule or frequency. Complete data about drug administration, including any overdose, regardless of whether the overdose was accidental or intentional, should be reported in the eCRF. See Section 10.1 for the reporting of adverse events associated with overdose.

7.3. Method of Treatment Assignment

The treatment assignment (randomization) will occur at the end of the Screening Period, once all the required screening procedures have been completed and all required data have been submitted to the Sponsor or its authorized representative. Upon receiving acknowledgment of subjects' eligibility from the Sponsor or its authorized representative, subject can be assigned for treatment using IRT. This study will utilize the IRT for randomization.

Designated research personnel at each investigational site will be assigned password protected, coded identification numbers which allows them to access the IRT to enroll subjects. For drug assignment at each dose start and in the event of any dose reduction, dose escalation site staff must contact IRT to record the new dose level and obtain the new study treatment assignment.

The relationship of the randomization number to the subject ID number will be described by a randomization algorithm. The randomization algorithm will be employed by the IRT system to assign a subject to a treatment based on the prespecified rules, such as double-blind study, stratified randomization with randomization ratio active versus placebo on a 2:1; subjects will be placed into the appropriate stratum per the responses/data entered/collected for questions collecting stratification and based on the combination of these data points, the IRT will place the subject in the next available slot within the appropriate stratum for that subject. The IRT will be utilized to ensure an equal weight central randomization based on block randomization method according to stratification factors defined in Section 3.1, Design of Study. The randomization number corresponds to a particular treatment arm within a stratum. The randomization number, by itself, will not unblind a user to the subject's treatment. The randomization number should be coupled with all the unblinded code information, in order the subject to become unblinded.

7.4. Packaging and Labeling

The label(s) for luspatercept will include Sponsor name, address and telephone number, the protocol number, IP name, dosage form and strength (where applicable), amount of IP per container, lot number, expiry date (where applicable), medication identification/kit number, dosing instructions, storage conditions, and required caution statements and/or regulatory statements as applicable. Additional information may be included on the label as applicable per local regulations.

7.4.1. Blinding

For this trial, all subjects, study site staff, and Celgene Corporation representatives with the exception of designated individuals (eg, the pharmacist at the investigational site), will remain blinded to all treatment assignments until all subjects enrolled in the study have completed 48 weeks of double-blind treatment or discontinued before reaching 48 weeks of double-blind treatment, whichever is the earlier date, or at the time the study is unblinded (per DMC recommendation) and the data base is locked.

The designated site individual (for example the pharmacist) at the investigational site will use a syringe (that exactly matches the syringe used for reconstituted luspatercept) and sterile normal saline (0.9% sodium chloride for injection) to prepare a matching placebo. Thus, the designated site individual at the investigational site will be unblinded and will give Investigators and their staff luspatercept and placebo in a blinded manner.

Randomization, drug dispensing, dose reduction/escalation, and drug discontinuation will be accomplished by an IRT system. Authorized site personnel must contact the IRT for randomization, study drug assignment at the beginning of each cycle, to register dose reductions or escalations, and treatment discontinuation. Confirmation of each call will be sent to the investigational site and Celgene.

For emergency unblinding, refer to Section [12.2](#).

7.5. Investigational Product Accountability and Disposal

Accountability for study drug that is administered during the course of the study is the responsibility of the Investigator or designee. Investigational clinical supplies must be received by a designated person at the clinical site and kept in a secure and temperature-controlled location. The investigational site must maintain accurate records demonstrating dates and amounts of study drug received, to whom it was administered (subject-by-subject accounting), and accounts of any luspatercept accidentally or deliberately destroyed or returned. Accurate recording of all IP administration will be made in the appropriate section of the subject's eCRF and source documents. Unless otherwise notified, all vials of study drug, both used and unused, must be saved for drug accountability. The used vials may be discarded, per the institution's standard practice, after drug accountability has been completed by the monitor. The Investigator must return all unused vials of study drug to the Sponsor at the end of the study, or the study drug may be destroyed at the clinical site with the permission of the Sponsor. For either scenario, the outcome must be documented on the drug accountability log. The Sponsor will provide direction for the outcome of all unused vials.

Celgene (or designee) will review with the Investigator and relevant site personnel the process for investigational product return, disposal, and/or destruction including responsibilities for the site versus Celgene (or designee).

7.6. Investigational Product Compliance

Study drug will be administered as a SC injection at the clinical site by the study staff. Monitoring for patient compliance with the treatment regimen is therefore unnecessary.

Accurate recording of all IP administration will be made in the appropriate section of the subject's eCRF and source documents.

The Investigator or designee is responsible for accounting for all IP that is administered during the course of the study.

9. STATISTICAL CONSIDERATIONS

9.1. Overview

The proposed Phase 2 study is a double-blind, randomized, placebo- controlled, multicenter study to determine the efficacy and safety of luspatercept (ACE-536) versus placebo in adult NTDT subjects. The study populations, study endpoints, and statistical plan are discussed below.

9.2. Study Population Definitions

Study populations to be analyzed are defined as follows:

Intent-to-treat (ITT): The ITT population will consist of all randomized subjects regardless of whether or not the subject received IP.

Per Protocol Set (PPS): Subjects in the ITT who have taken at least 1 dose of IP and do not have major protocol deviations (details will be specified in the SAP prior to database [DB] lock). The PPS population might be used in addition to ITT population to analyze primary and secondary endpoints as detailed in the SAP.

Safety: The safety population will consist of all subjects who were randomized and received at least 1 dose of IP. Subjects will be included in the treatment group corresponding to the IP they actually received.

QoL Evaluable Population: The QoL evaluable population consists of all subjects in the ITT population who completed the health-related QoL assessment at baseline (screening) and at least one postbaseline assessment visit.

Statistical methods to handle missing data will be described in the SAP. The SAP will also describe detailed rules for data handling and analysis (eg, time windows, visit-by-visit analysis, endpoint analysis, protocol deviations).

9.3. Sample Size and Power Considerations

Based on the assumption of a targeted primary endpoint response rates at least 50% in the luspatercept group and 10% for the placebo group, and 2:1 randomization, a total sample size of 150 (100 in the luspatercept group, 50 in the placebo group) will have at least 99% power to detect the difference between the 2 groups with a 2-sided alpha of 0.05 and assumed 10% drop-out rate.

For NTDT-PRO T/W domain scores, assume the mean change from baseline scores at Week 24 are 1.2 and 0.5 for luspatercept and placebo group, respectively, with a common standard deviation of 1.2, the statistical power will be 91%.

Randomization and Stratification

Subjects will be randomized to receive luspatercept or placebo at a 2:1 ratio. Randomization will be accomplished by an IRT to ensure timely registration and randomization. A stratified block randomization schedule will be implemented. Randomization will be stratified by:

Baseline hemoglobin level

- ≥ 8.5 g/dL
- < 8.5 g/dL

Baseline NTDT-PRO T/W score

- ≥ 3 points
- < 3 points

9.4. Background and Demographic Characteristics

Subjects' age, height, weight, and baseline characteristics will be summarized using descriptive statistics, while gender, race, and other categorical variables will be provided using frequency tabulations by dose cohort. Prior transfusion history will be summarized. Medical history data will be summarized using frequency tabulations by Medical Dictionary for Regulator Activities (MedDRA) system organ class and preferred term. Beta-thalassemia diagnoses as well as RBC transfusion burden will be summarized using frequency tabulations.

9.5. Subject Disposition

Subject disposition (analysis population allocation, entered, discontinued, along with primary reason for discontinuation) will be summarized using frequency and percent for both treatment and follow-up phases. A summary of subjects enrolled by site will be provided. Protocol deviations will be summarized using frequency tabulations.

9.6. Efficacy Analysis

Primary analysis will be done after ALL subjects completed 48 weeks or discontinued earlier. Then at the end of the OLP phase, updated safety and efficacy analysis will be done.

9.6.1. Primary Efficacy Analysis

The primary efficacy endpoint of this study is erythroid response, defined as an increase from baseline ≥ 1.0 g/dL in mean of hemoglobin values over a continuous 12-week interval from Weeks 13 to 24 in the absence of transfusions.

The Hb values within 21 days following a transfusion may be influenced by the transfusion and will be excluded from this analysis. Baseline Hb is the average of 2 or more Hb measurements at least 1 week apart within 4 weeks before Dose 1. For discontinued subjects who do not complete 24 weeks of the Double-blind Treatment Period, Hb data will continue to be collected (see [Table 3](#)).

The primary efficacy analysis will be performed on the ITT population. Cochran-Mantel-Haenszel (CMH) test will be performed with randomization stratification factor(s) in the model to compare the treatment and placebo groups at 2-sided 0.05 level; the corresponding 95% confidence interval for odds ratio will also be provided.

For a subject, if the Hb average over Weeks 13-24 interval cannot be calculated due to missing data, the closest Hb 12-week average will be used.

Sensitivity analysis: If a subject has less than 3 Hb measurements from Week 13 (-7 days) to Week 24 (+7 days), he/she will be considered as non-evaluable. Similar approach will be followed for Hb secondary endpoints over Weeks 37 to 48.

9.6.2. Key Secondary Efficacy Analysis

The analyses of key secondary efficacy endpoints will be performed on the ITT population. The three key secondary endpoints are as follows:

- 1) Mean change from baseline in NTD-T-PRO Tiredness and Weakness (T/W) domain score over a continuous 12-week interval from Week 13 to Week 24.
- 2) Mean change from baseline in mean of hemoglobin values over a continuous 12-week interval from Week 13 to Week 24 in the absence of transfusions.
- 3) Proportion of subjects who have an increase from baseline ≥ 1.0 g/dL in mean of hemoglobin values over a continuous 12-week interval from Week 37 to Week 48 in the absence of transfusions.

To control the overall Type 1 error rate for three key secondary endpoints, the testing procedure will be implemented strictly in order: after the result from the primary efficacy analysis in the ITT population shows statistical significance, the key secondary endpoint 1 will be tested next. The key secondary endpoint 2 will be tested only if the test results for both primary endpoint and the key secondary endpoint 1 are significant. The key secondary endpoint 3 will be tested only if the test results for primary endpoint and the key secondary endpoints 1 and 2 are all significant. The details of the multiplicity control will be specified in the SAP.

9.6.2.1. NTD-T-PRO (T/W Domain) Mean Change Between Weeks 13 to 24

Mean NTD-T-PRO (T/W domain) change from baseline over a 12-week window between Weeks 13 to 24 will be analyzed using analysis of covariance (ANCOVA) method with treatment group and randomization stratification factor(s) in the model score as covariates.

9.6.2.2. Hemoglobin Mean Change Between Weeks 13 to 24

Mean Hemoglobin change from baseline over 12-week window between Weeks 13 to 24 during the treatment period will be analyzed using ANCOVA method with treatment group and randomization stratification factor(s) in the model value as covariates.

9.6.2.3. Hemoglobin Response Between Weeks 37 to 48

Hemoglobin responder between Weeks 37 to 48, defined as an increase from baseline ≥ 1.0 g/dL in mean of hemoglobin values over a continuous 12-week interval from Weeks 37 to 48 in the absence of transfusions.

The CMH test will be performed with randomization stratification factor(s) in the model to compare the luspatercept and placebo groups at 2-sided 0.05 level; the corresponding 95% confidence interval for odds ratio will also be calculated.

Analysis similar to the primary analysis will be performed.

9.6.3. Secondary Efficacy Analysis

9.6.3.1. FACIT-F Fatigue Subscale: Mean Change from Baseline between Weeks 13 to 24 and Weeks 37 to 48

Mean FACIT-F Fatigue subscale change from baseline over a 12-week window between Weeks 13 to 24 will be analyzed using ANCOVA method with treatment group, randomization stratification factor(s) in the model and baseline FACIT-F Fatigue subscale score as covariates.

Mean change from baseline for Weeks 37 to 48 will be analyzed similarly.

9.6.3.2. NTDT-PRO SoB Domain: Mean Change from Baseline between Weeks 13 to 24 and Weeks 37 to 48

Mean NTDT-PRO SoB Domain from baseline over a 12-week window between Weeks 13 to 24 will be analyzed using ANCOVA method with treatment group, randomization stratification factor(s) in the model and baseline NTDT-PRO SoB scores covariates. Similar analysis will be performed for Weeks 37 to 48.

9.6.3.3. Hemoglobin Mean Change Between Weeks 37 to 48

Mean Hemoglobin change from baseline over 12-week window between Weeks 37 to 48 during the treatment period will be analyzed using ANCOVA method with treatment group, randomization stratification factor(s) in the model as covariates.

9.6.3.4. NTDT-PRO (T/W Domain) Mean Change Between Weeks 37 to 48

Mean NTDT-PRO (T/W domain) change from baseline over a 12-week window between Weeks 37 to 48 will be analyzed using analysis of covariance (ANCOVA) method with treatment group, randomization stratification factor(s) in the model as covariates.

9.6.3.5. Definition of NTDT-PRO Minimum Clinical Important Difference (MCID) and Responder Definition (RD) Thresholds

The minimum clinical important difference (MCID) is the amount of difference in a PRO measure between treatment groups in a clinical trial that will be interpreted as a treatment benefit. The responder definition (RD) threshold is the individual subject score change over a predetermined time period that will be interpreted as a treatment benefit. In case of MCID and RDRD thresholds for the NTDT-PRO will be primarily determined with longitudinal anchor-based methods prior to database lock and unblinding using data collected over a 12-week window between Weeks 13 to 24. Distribution-based methods will also be used as additional supporting evidence. Anchors to be considered include the PGI-C, PGI-S, SF-36v2 Vitality and Physical Functioning scales, and FACIT-F score. PGI-S is included as an extra item administered at the end of each NTDT-PRO assessment (see Section 6.8).

After the database lock and unblinding, statistical analysis will be performed for unblinded data. Proportion of subjects with a decrease from baseline \geq RD in mean NTDT-PRO T/W score, over Weeks 13 to 24 and Weeks 37 to 48 in the luspatercept group will be compared with the placebo group. The CMH test will be used with baseline NTDT-PRO T/W category ≥ 3 versus < 3 as the stratum to compare the response rates between the 2 groups. The corresponding 95% confidence interval for odds ratio will also be provided.

9.6.3.6. FACIT-F Fatigue Subscale: Response at Weeks 13 to 24 and Weeks 37 to 48

Proportion of subjects with an increase from baseline ≥ 3 in mean FACIT-F Fatigue subscale (FS) score, over Weeks 13 to 24 and Weeks 37 to 48 in the luspatercept group will be compared with the placebo group. The CMH test will be used with baseline FACIT-F Fatigue subscale category ≥ 37 versus < 37 as the stratum to compare the response rates between the 2 groups. The corresponding 95% confidence interval for odds ratio will also be provided.

Similar analysis will be performed for Weeks 37 to 48.

9.6.3.7. SF-36 v2: Mean Change from Baseline at Week 24 and Week 48

The SF-36 Version 2.0 (acute condition with 1-week recall period) is a self-administered instrument consisting of 8 multi-item scales that assess 8 health domains: Physical functioning, Role-Physical, Bodily Pain, General Health, Vitality, Social functioning, Role-Emotional, and Mental Health. Two overall summary scores (Physical Component and Mental Component) can also be obtained.

Summary statistics for the PCS and MCS norm-based scores, as well as change from baseline in these scores, will be assessed at Weeks 12, 24, 36, and 48. Scoring for the SF-36 and methods to address missing values will be accomplished according to directions provided by the instrument developers.

A mixed effect repeated measure model will be used with subjects as the random effect. The model includes the change from baseline scores up to Week 24 and 48 as the outcome, and treatment group assignment, time, baseline scores, randomization stratification factor(s), time-by-baseline score, and time-by-treatment group assignment in the model. If any of the interaction terms are not significant, it will be excluded from the final model.

9.6.3.8. LIC / ICT: Responder Analysis at Week 24 and Week 48

There are 3 scheduled LIC measurements for each subject: baseline, Weeks 24 and 48. For subjects who discontinued before 48 weeks the LIC and ICT data may be collected in the PTFP.

ICT daily dosing data will be collected during the study.

At Week 24 or Week 48, a LIC/ICT responder will be defined as one of the following:

- Baseline LIC (by MRI) ≥ 3 mg/g dw: $\geq 20\%$ reduction in LIC, OR, $\geq 33\%$ decrease in ICT daily dose
- Baseline LIC < 3 mg/g dw: no increase in LIC > 1 mg/g dw AND not starting treatment with ICT or no increase in ICT daily dose $\geq 33\%$, if on ICT at baseline

CMH test will be performed with baseline ICT use (Yes, No) and randomization stratification factor(s) as the strata adjusted to compare the luspatercept and placebo groups at 2-sided 0.05 level; the corresponding 95% confidence interval for odds ratio will also be calculated.

9.6.3.9. Serum Ferritin: Mean Change from Baseline at Week 24 and Week 48

Serum ferritin change from baseline at Week 24 will be analyzed using ANCOVA method with treatment group and randomization stratification factor(s) in the model and baseline Serum ferritin as the covariate.

If the normality assumption is significantly deviated, the nonparametric Wilcoxon rank-sum test will be used instead.

Mean change at week 48 will be analyzed similarly.

9.6.3.10. Liver Iron Concentration: Mean Change from Baseline at Weeks 24 and 48

LIC mean change from baseline will be analyzed using ANCOVA method with treatment group and randomization stratification factor(s) in the model and baseline Liver Iron Concentration as the covariate.

LIC mean change from Baseline at Week 48 will be analyzed similarly.

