Mean NTDI-PRO (T/W domain) change from baseline over a 12-week interval between Weeks 37 to 48 (nominal Dose 13 to Dose 17) will be analyzed using ANCOVA method with treatment group and randomization stratification factor(s) in the model as covariates.

The treatment-by-stratification-factor(s) interaction will be added to the ANCOVA model as a sensitivity analysis and results from this model will be compared to the primary fixed effects model (without the interaction effect). If the interaction is significant at a 2-sided 0.1-alpha level, the nature of this interaction will be inspected as to whether it is quantitative (that is, the treatment effect is consistent in direction but not in size of effect) or qualitative (the treatment is beneficial in some values of the stratification factor(s)). If the interaction effect is found to be quantitative, results from the primary fixed effect model will be presented. If the interaction effect is found to be qualitative, further inspection will be used to identify in what values of the stratification factor(s) the treatment is more beneficial.

10.4.5 FACIT-F Fatigue Subscale (FS) Response at Weeks 13 to 24 and Weeks 37 to 48

Proportion of subjects with an increase from baseline ≥ 3 in mean FACIT-F FS score, over Weeks 13 to 24 in the luspatercept group will be compared with the placebo group. The CMH test will be used with baseline FACIT-F FS category ≥ 37 versus < 37 as the stratum to compare the response rates between the 2 groups. The selection of 37 as a threshold is based on a Phase 2 Luspatercept study (A536-06) in which it corresponds to a NTDI-PRO T/W domain scores of 4. The corresponding 95% confidence interval for odds ratio will also be provided. Similar analysis will be performed for Weeks 37 to 48.

10.4.6 SF-36 v2: Mean Change from Baseline at Week 24 and Week 48

The SF-36 Version 2.0 (acute condition with 1-week recall period) is a self-administered instrument consisting of 8 multi-item scales that assess 8 health domains: Physical functioning (PF), Role-Physical (RP), Bodily Pain (BP), General Health (GH), Vitality (VT), Social functioning (SF), Role-Emotional (RE), and Mental Health (MH). Two overall summary scores, Physical Component Summary (PCS) and Mental Component Summary (MCS), will be calculated from the 8 health domains. The primary interests of the SF-36 are the PCS and MCS norm-based scores.

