The responder definition (RD) threshold is the individual subject score change over a predetermined time period that will be interpreted as a treatment benefit. The RD threshold of 1 for the NTDT-PRO is jointly determined by longitudinal anchor based and distribution-based methods prior to database lock using data collected over a 12-week window between Weeks 13 to 24 ([REDACTED]).

Proportion of subjects with a decrease from baseline \geq RD (=1) in mean NTDT-PRO T/W score, over Weeks 13 to 24 and Weeks 37 to 48 in the luspatercept group will be compared with the placebo group. The CMH test will be used with baseline NTDT-PRO T/W category ≥ 3 versus <3 as the stratum to compare the response rates between the 2 groups. The corresponding 95% confidence interval for odds ratio will also be provided.

The cumulative distribution function (CDF) of observed changes in NTDT-PRO T/W over a continuous period of Weeks 13 to 24 and Weeks 37 to 48 from baseline will be generated by treatment group. The CDF curve presents the entire distribution of responses and shows a continuous plot of the entire range of changes from baseline at a given post-baseline visit on the x-axis and the cumulative percentage of subjects experiencing a change up to a particular level on the y-axis.

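### The T/W and FACIT-F responder tests put subjects whose baseline rules out a response in the same CMH stratum as subjects who can respond; for T/W this costs about 1 to 6 points of power if an assumed 4-20% of subjects are at the floor

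*Protocol*

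**What the plan says.** Protocol 9.6.3.5 compares T/W response rates between arms: "The CMH test will be used with baseline NTDT-PRO T/W category" at or above 3 versus below 3 as the stratum. It leaves the responder threshold open. SAP 10.4.16 sets it at a decrease of 1: "The RD threshold of 1 for the NTDT-PRO is jointly determined by longitudinal anchor based and distribution-based methods". It keeps the same two strata.

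Protocol 9.6.3.6 defines FACIT-F response as a rise of at least 3 in the mean FS score: "The CMH test will be used with baseline FACIT-F Fatigue subscale category" at or above 37 versus below 37. SAP 10.4.5 repeats this: "The CMH test will be used with baseline FACIT-F FS category" with the same cut.

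SAP 18.3.1 gives the weekly T/W score a range of 0 to 10. SAP 18.3.2 scores FACIT-F items 0 to 4 and lists 13 items for FS, so the maximum is 52. The eligibility criteria (Protocol 4.2 and 4.3) require no minimum symptom level, and the randomisation stratum below 3 runs down to 0.

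Both endpoints are listed as other secondary endpoints (SAP 4.2.2.2), outside the sequence in SAP 10.1. No power is stated for either.

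**The concern.** A T/W mean cannot go below 0, so the largest possible fall equals the baseline. Anyone starting below 1 is a non-responder by construction. Likewise, anyone starting above 49 on FS cannot gain 3, because 52 - 3 = 49. Neither the cut at 3 nor the cut at 37 separates these subjects: all those at the T/W floor sit in the lower T/W stratum, and all those at the FS ceiling in the upper FS stratum.

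Inside those strata they carry no information on treatment but add to the variance the CMH test assigns. Power is lost, and the odds ratio is pulled towards 1. The reported response rate also depends on how many nearly symptom-free subjects were enrolled, which makes it harder to read as a measure of individual benefit.

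**Working it through.** **Inputs from the documents** (Protocol 9.3): "a total sample size of 150 (100 in the luspatercept group, 50 in the placebo group) will have at least 99% power"; "with a 2-sided alpha of 0.05 and assumed 10% drop-out rate"; "Subjects will be randomized to receive luspatercept or placebo at a 2:1 ratio"; and for T/W, "assume the mean change from baseline scores at Week 24 are 1.2 and 0.5 for luspatercept and placebo group", with a common SD of 1.2.

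**The plan's own figure.** The only patient-reported-outcome power stated is 91%, for the T/W mean change. With SE = 1.2 × √(1/100 + 1/50) = 0.2078, power = Φ(0.7/0.2078 - 1.96) = Φ(1.41) = 92.0%. With 90 and 45 subjects after 10% drop-out it is 89.2%. The stated figure is reproduced within 2 points.

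**Implied T/W response rates.** With normal changes, P(fall ≥ 1) is:
- luspatercept: Φ((1.2 - 1)/1.2) = 56.6%
- placebo: Φ((0.5 - 1)/1.2) = 33.8%

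These are taken as the rates among subjects able to respond.

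**Assumptions not in the documents.** f is the share of subjects with baseline T/W below 1, and s is the share in the stratum below 3 (30-50%). Both are the same in each arm.

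**Formula.** In each stratum with n1 and n2 subjects, N = n1 + n2, w = n1·n2/N and m expected responders:
- D = w(p1 - p2)
- V0 = n1·n2·m(N - m)/[N²(N - 1)]
- V1 = w²[p1(1 - p1)/n1 + p2(1 - p2)/n2]

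Summing over strata, power = Φ((D - 1.96√V0)/√V1).

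**Worked case, f = 10%, s = 40%, 100 versus 50.**

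| Stratum | n1 / n2 | Rates | D | V0 | V1 |
|---|---|---|---|---|---|
| T/W ≥ 3 | 60 / 30 | 56.6% / 33.8% | 4.554 | 5.054 | 4.623 |
| T/W < 3, as planned | 40 / 20 | 42.5% / 25.4% | 2.277 | 3.153 | 2.769 |
| T/W 1 to < 3 only | 30 / 15 | 56.6% / 33.8% | 2.277 | 2.556 | 2.311 |

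- As planned: D = 6.832, V0 = 8.207, V1 = 7.392; power = Φ(0.448) = 67.3%.
- Floor subjects separated: D = 6.832, V0 = 7.610, V1 = 6.934; power = Φ(0.541) = 70.6%.

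D is the same in both. The gain comes from removing variance contributed by subjects whose outcome is fixed.

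**Range over the assumptions (100 versus 50, s = 30-50%).**

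| f | Planned strata | Floor separated | Gain, points |
|---|---|---|---|
| 0% | equal | equal | 0 |
| 4% | 72.0% | 73.5% | 1.4-1.5 |
| 5% | 71.1-71.3% | 73.0% | 1.7-1.9 |
| 10% | 67.1-67.6% | 70.6% | 2.9-3.5 |
| 15% | 63.1-64.5% | 68.0% | 3.5-4.9 |
| 20% | 59.4-62.0% | 65.2% | 3.2-5.8 |

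Sensitivity, all for f = 5-20%:
- With 90 versus 45 subjects the gains are 1.8 to 5.7 points.
- With rates among those able to respond between 30% vs 10% and 50% vs 30%, the gains are 0.6 to 4.5 points.
- If 56.6% and 33.8% are read as all-subject rates instead, the gains are 1.8 to 7.6 points. At f = 20% that requires 56.6/0.8 = 70.8% response among those able to respond.

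Simulation with drawn baselines (4,000 trials per scenario, 4-10% at the floor) gave gains of 0.9 to 3.5 points. A third stratum gave the same power as leaving floor subjects out.

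**Response rate.** The all-subject rate is (1 - f) times the rate among those able to respond. At f = 10% it is 51.0% vs 30.5%, against 56.6% vs 33.8%. The crude odds ratios are 2.37 and 2.55.

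**Type I error.** A floor subject is a non-responder in either arm, and the added stratum depends on baseline only. Simulated null rejection was 4.7% and 4.8% for the two analyses.

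**FACIT-F.** The same algebra applies at FS above 49. The documents give no FS effect, SD or baseline distribution, so no figure is computed.

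**The case against.** **The size rests on an unknown.** The documents do not say how many subjects start below 1. This stands: the cost is conditional, is zero if nobody is at the floor, and approaches 6 points only when about 20% are nearly symptom-free. Simulations that draw the planned changes and clip them at zero also move away from the plan as the floor share grows: at 4% the realised means are about 1.12 vs 0.47, and at 22% about 0.90 vs 0.36, against the planned 1.2 vs 0.5. The smaller figures are the ones closest to the planning assumptions.

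**A reader might infer that the reported response rate is biased.** It is not. The endpoint is the proportion of subjects with the change, and the planned rate is correct for that population. The rate among subjects able to respond is a different estimand.

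**A reader might carry the T/W range over to FACIT-F.** The documents give no inputs for that.

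**Much is already in place.** The strata confine floor and ceiling subjects to one stratum each, SAP 10.4.16 plans a cumulative distribution plot of T/W change, and mean changes are analysed separately. This limits the consequence. But the calculation above already includes the planned strata, and the plot does not change the test or the odds ratio. SAP 10.4.6 and 14 also defer further quality-of-life sensitivity and subgroup analyses to a separate plan that is not available here, so it cannot be said that no restricted analysis exists anywhere.

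**Keeping everyone in the test is partly nominal.** A stratum with no possible responders adds nothing, so the odds ratio would describe subjects able to respond. This is true and should be stated in the SAP.

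**Conclusion.** The point holds as a modest loss of efficiency. The cut-offs of T/W below 1 and FS above 49 follow directly from the score ranges and thresholds, and the planned strata do not separate these subjects. For T/W the loss is about 1 to 6 points of power if an assumed 4-20% of subjects start below 1. This rests on the plan's 1.2 vs 0.5 with SD 1.2 applying to subjects able to respond, and on the planned arm sizes. It is zero with no floor subjects and 0.6 to 4.5 points at lower response rates. For FACIT-F only the direction can be stated.

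The documents do not support a stronger reading. Neither test is invalid, type I error is unaffected, and no primary or key secondary conclusion depends on these endpoints. It is worth considering because it is inexpensive, not because the planned analysis is wrong.

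**What to change.** Consider this change in Protocol 9.6.3.5 and 9.6.3.6 and in SAP 10.4.16 and 10.4.5:

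- Use three baseline strata in each CMH test: T/W below 1, 1 to below 3, and 3 or above; FS below 37, 37 to 49, and above 49.
- Keep the all-subject response rate as the endpoint.
- Report the number of subjects with baseline T/W below 1 and FS above 49 in each arm, and the response rate among subjects able to respond as supportive.
- State that the added stratum contributes nothing to the CMH statistic or the odds ratio, so the odds ratio describes subjects able to respond.

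The cost is a short addition to each section and one derived baseline category per instrument. No new data are needed. The floor and ceiling shares can be counted from blinded baseline data before database lock, which would settle the main unknown in the T/W sizing and show whether the change matters.
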